9.5. Infusion Premedication

Premedication administered before infusion or during infusion or not used (collected in Drug Administration CRF) will be tabulated in a data listing to present longitudinally for all scheduled visits (every two weeks).

The number of patients with or without premedication use will be summarized by visit for overall and by gender.

Note to programmer: this analysis is based on data captured in the CM dataset where CMSCAT = ‘Premedication’.

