TEST PRODUCT(S), DOSE AND MODE OF ADMINISTRATION: During the first 3 months (Screening period), patients will be on agalsidase alfa according to their previous regimen (dose, frequency and rate of infusion). Upon confirmation of eligibility, patients will be switched to PRX-102 1 mg/kg, intravenously to be administered over 3 hours, every 2 weeks. After the first 2 months of treatment with PRX-102, infusion time may be reduced gradually to 1.5 hours pending patient tolerability, investigator evaluation, and Sponsor Medical Monitor/Director approval.

STUDY DURATION: Total 15 months, with 3 months Screening while on agalsidase alfa and 12 months Treatment on PRX-102, with the option to be enrolled in an extension study upon completion of this study.

DISCONTINUATION FROM TREATMENT:

Reasons for permanent discontinuation include the following:

- The subject experiences two or more Grade 3 toxicities or one or more Grade 4 toxicity considered by the investigator associated with PRX-102 treatment (CTCAE v. 4.03, 2010)
- The subject experiences progressive hypersensitivity or severe hypersensitivity that is not allayed with pre-treatment
- The subject requests to discontinue treatment
- The Investigator feels that it is not in the best interest of the subject to continue treatment and/or if the investigator believes that the subject can no longer be compliant with the requirements of the study

SAFETY ENDPOINTS:

Change from baseline in:

- Clinical laboratory tests
- Physical examination
- Assessment of the injection site
- Electrocardiogram
- Treatment-emergent adverse events
- Ability to taper off infusion premedication throughout the first 2 months of the study
- Requirement for use of premedication overall to manage infusion reactions
- Treatment-emergent anti-PRX-102 antibodies

EFFICACY ENDPOINTS:

- Mean annualised change in estimated glomerular filtration rate (eGFR_{CKD-EPI})

- Left Ventricular Mass Index (g/m^2) preferably by MRI (echocardiogram can be used as an alternative)
- Plasma Lyso-Gb3
- Plasma Gb3
- Urine Lyso-Gb3
- Protein/Creatinine ratio spot urine test
- Frequency of pain medication use
- Exercise tolerance (Stress Test)
- Short Form Brief Pain Inventory (BPI)
- Mainz Severity Score Index (MSSI)
- Quality of life EQ-5D-5L

STATISTICAL ANALYSIS:

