3.2. Endpoints

3.2.1. Safety Endpoints

- Change from baseline in:
 - Clinical laboratory tests
 - Physical examination
 - Electrocardiogram
- Treatment-emergent adverse events
- Assessment of the injection site and infusion-related reactions (IRR), as part of the adverse events
- Ability to taper off infusion premedication after switch to pegunigalsidase alfa
- Requirement for use of premedication overall to manage infusion reactions
- Treatment-emergent anti-pegunigalsidase alfa antibodies

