5. ANALYSIS POPULATION

5.1. Safety Population

The safety population (SP) consists of all subjects who received any dose of pegunigalsidase alfa in the study. All safety analyses will be based on this population.

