8.3. Baseline Characteristics

The baseline characteristics will be summarized by descriptive statistics overall and by each of the subgroups described in section 7.4. The analysis will be repeated for the Safety and Efficacy sets.

Continuous variables:

- Age started Fabry therapy
- % residual enzyme activity in leukocyte (defined as the value in leukocyte \times 100/83.5, where 83.5 is the mean of reference range)
- % residual enzyme activity in plasma (defined as the value in plasma \times 100/12.95, where 12.95 is the mean of reference range)
- eGFR
- pre-switch eGFR annualized slope
- Plasma Lyso-Gb3
- Plasma Gb3
- Urine Lyso Gb3

Categorical variables:

- Fabry disease (FD) classification (classic / non-classic) (See Section 7.4)
- UPCR classified into four categories (See Section 10.4)
- Presence of Proteinuria (UPCR \geq 0.5 gr/gr / $<$ 0.5 gr/gr)
- Treatment with ACEi or ARBs (yes/no). Status is yes if there is any concomitant medication of ACE or ARB taken before baseline visit, otherwise it will be determined based on the answer to the question ‘patient is NOT treated with an ACE inhibitor or ARB’.
- Premedication use (yes / no: premedication used for agalsidase alfa infusions before enrolment)
- anti Replagal Immunogenicity status (ADA-positive or ADA- negative to agalsidase alfa (REPLAGAL). The determination of the status is based on the results of the IgG Screening for REPLAGAL.
- anti pegunigalsidase alfa Immunogenicity status (ADA-positive or ADA- negative to pegunigalsidase alfa. The determination of the status is based on the results of the IgG Screening for PRX-102.

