14.3.5.3.1	Electrocardiography (ECG) for Overall and by Gender	Safety
14.3.5.3.2	Electrocardiography (ECG) – Shift from Baseline for Overall and by Gender	Safety
14.3.5.4.1	Number of Subjects Used Concomitant Medications for Overall and by Gender	Safety
14.3.5.4.2	Number of Subjects Used Pain Medications for Overall and by Gender	Safety
14.3.5.4.3.1	Number of Subjects Treated with ACEi and/or ARBs for Overall and by Gender	Safety
14.3.5.5.1	Infusion Premedication for Overall and by Gender	Safety

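### SAP 9.5 counts premedication users per visit among all treated patients, which does not estimate how many entry users were able to taper off

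*SAP*

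**What the plan says.** SAP 3.2.1 lists two separate premedication endpoints under safety, which is the primary objective. One is "Ability to taper off infusion premedication after switch to pegunigalsidase alfa". The other is "Requirement for use of premedication overall to manage infusion reactions". The protocol synopsis words the first with a time window: "Ability to taper off infusion premedication throughout the first 2 months of the study".

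SAP 9.5 plans two displays. One is a per-patient listing of premedication at each scheduled infusion. The other is the only summary: "The number of patients with or without premedication use will be summarized by visit for overall and by gender". The table list in SAP 11.1 has one matching entry, Table 14.3.5.5.1, "Infusion Premedication for Overall and by Gender", in the Safety population. SAP 5.1 defines that population as everyone given any dose and adds: "All safety analyses will be based on this population".

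Entry status is recorded. SAP 8.3 has a yes/no baseline characteristic for "premedication used for agalsidase alfa infusions before enrolment". SAP 9.5 does not use it as a denominator or a subgroup. The SAP gives no definition of a successful taper, no time point for judging it, no shift table of premedication use, and no count of patients who resume or newly start.

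**The concern.** A patient who was not on premedication at entry has nothing to taper, so the natural denominator for the taper endpoint is the entry users. The planned count puts everyone together at each visit and reports only the net number of users.

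Four different movements feed that number: entry users who come off, entry users who come off and go back on, non-users who start, and users who leave the study. The protocol allows for all of them. Section 6.2 says only some agalsidase alfa patients are premedicated, and that premedication may be kept or brought back. Appendix 3 lets premedication be considered after early signs of hypersensitivity on PRX-102, without limiting this to previous users. Under section 6.3.4 withdrawn patients are not replaced, and SAP 7.2 imputes no missing endpoint values.

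At stake is whether the study report can state how many patients who needed premedication on agalsidase alfa managed without it on PRX-102. Followed as written, the plan produces no table with that number.

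**Working it through.** **Inputs.** Planned N = 22 (SAP 4.1, Protocol 10.1). The plan states no target or expected rate for premedication, so there is no figure of its own to reproduce. Let k be the entry users, t the entry users off premedication at a later visit, and s the entry non-users on it at that visit. The documents give none of these, so every value below is an assumption.

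**Step 1. What each quantity measures (complete follow-up).**
- Planned table: k/22 at Visit 1, then (k − t + s)/22 later.
- Taper endpoint: t/k.
- New starts: s/(22 − k).

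The planned table fixes only the difference t − s.

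**Step 2. Which taper rates fit a given table.**
- 6 users at Visit 1 and 6 later: t = s, so t can be 0 to 6. The rate is anything from 0% to 100%.
- 6 falling to 4: t = s + 2, so t can be 2 to 6. The rate is 33.3% to 100%.
- 11 falling to 7: t = s + 4, so t can be 4 to 11. The rate is 36.4% to 100%.

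One constructed case with full cancelling: k = 6, t = 4, s = 4. The planned table stays at 6/22 (27.3%), while 4/6 (66.7%) tapered and 4/16 (25.0%) newly started.

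**Step 3. Withdrawals.** Take 6 users and 16 non-users at Visit 1, and two withdrawals.
- Case A: two entry users taper and two entry non-users leave. Users: 6 − 2 = 4. Non-users: 16 + 2 − 2 = 16.
- Case B: nobody tapers and two entry users leave. Users: 6 − 2 = 4. Non-users: 16.

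Both cases show 4 with and 16 without. The taper rate is 2/6 (33.3%) in A and 0/6 (0%) in B.

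**Step 4. Dilution when nobody starts or withdraws (s = 0).** The visible fall is t/22 = (k/22) × (t/k). With about two thirds tapering:

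| k | t | Planned table | Fall (points) | t/k | Exact 95% CI |
|---|---|---|---|---|---|
| 3 | 2 | 13.6% to 4.5% | 9.1 | 66.7% | 9.4 to 99.2% |
| 6 | 4 | 27.3% to 9.1% | 18.2 | 66.7% | 22.3 to 95.7% |
| 11 | 7 | 50.0% to 18.2% | 31.8 | 63.6% | 30.8 to 89.1% |
| 20 | 13 | 90.9% to 31.8% | 59.1 | 65.0% | 40.8 to 84.6% |

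Dilution is strong when entry users are few and mild when nearly everyone is one. In this setting the count itself is adequate: the fall in the number of users equals t, and k can be read from the Visit 1 row.

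**The case against.** Several points on the other side are sound.

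- **Overall requirement is summarised.** A reader might infer that both premedication endpoints lack a valid summary. They do not. Use per visit among all treated patients is a direct, if basic, summary of overall requirement, and the all-patient denominator suits it.
- **Dilution and cancelling are conditional.** A reader might infer that non-users will swamp the count, or that tapers and new starts will cancel. The documents give no number of entry users, tapers or starts, so neither can be asserted.
- **The data will be visible.** Premedication is continued through the first PRX-102 infusion (SAP 4), so the Visit 1 row should approximate the entry users. The SAP 9.5 listing shows each patient at each infusion. The SAP 9.8 listing gives start and end dates and whether a drug was taken before the first infusion. With 22 patients a reader could count by hand.
- **Harm is tracked elsewhere.** A reader might infer that reactions leading to new premedication would be hidden. Adverse events are summarised by time from infusion (SAP 9.1.4), and infusion-related reactions by event and by patient (SAP 9.1.5).
- **Layout and timing.** Table shells are in a separate document (SAP 12). The SAP also postdates an interim analysis at about 80% of patients (SAP 7.5), so any success definition added now follows sight of most of the data in an open-label trial. The SAP's endpoint wording drops the two-month window, and the SAP prevails over the protocol (SAP 2).

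These points limit the concern without removing it. A hand count from listings has no stated definition of success and no rule for resumption or withdrawal. Neither SAP 9.5 nor the table title promises a split by entry use. The Visit 5 time point is not arbitrary: Protocol 9.1.5 ends the taper there, Appendix 8 equates the two months with five infusions, and SAP 4 still describes a taper over the first two months.

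**Conclusion.** The concern holds for the taper endpoint only. The planned by-visit count does not estimate it, because the entry-user denominator is absent and only net use is shown. Once any patient starts or resumes, or an entry user withdraws, the taper rate cannot be recovered from the table; in the 6-to-6 example it is wholly undetermined. If none of these happens, the count gives the number tapered correctly, diluted only as a percentage of all patients.

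The size in this trial cannot be stated, because it depends on numbers that the documents do not give. The endpoint is descriptive, so no test or interval in the plan is affected. This is a worthwhile reporting correction to a named safety endpoint. It does not threaten the safety conclusions as a whole.

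**What to change.** Keep the by-visit table as the summary of overall requirement. Add to SAP 9.5 and the table list one descriptive table, or an equivalent shift table, split by the entry status already defined in SAP 8.3:

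- **Entry users (N = all entry users):** n/N off premedication at Visit 5; n/N still off at Visit 27; n/N who came off and later resumed. For a patient who left early, give status at the last infusion in a separate row.
- **Entry non-users:** n/N who ever started premedication on PRX-102.
- **Withdrawals:** show patients who left before each time point in their own row, and do not count them as tapered.
- **Data source:** name one. SAP 9.5 cites the Drug Administration CRF for the listing, while its programmer note points to the CM dataset.
- **Status:** label the table as added after the interim analysis. SAP 7.5 already provides for new analyses at the final stage.

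Exact confidence intervals are optional; with few entry users they will be wide (22.3 to 95.7% for 4/6).

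The SAP already does this for a parallel question: section 10.10 plans yes/no and number-used shift tables for pain medication from baseline to last visit. The cost is one short table from data already collected, with no new assessments and no change to any inferential result.

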9.6. Treatment-emergent Anti-Pegunigalsidase alfa Antibodies

Treatment emergent anti-pegunigalsidase alfa antibodies (ADA+ vs. ADA-) is defined in Section 7.4.

The number and percentage of patients who are Treatment emergent ADA will be summarized by visit

An overall anti-pegunigalsidase alfa antibodies status per patient during the study (“positive” if positive at any visit, negative if negative at all visits), will be summarized as well.

Analyses will be repeated by gender and by Fabry disease classification (classic/non-classic).

Note to programmer: The treatment-emergent anti-pegunigalsidase alfa antibodies (ADA) including the three test results:

- a. IgG = negative if ‘IgG Screening (Presumptive Pos/Neg)’ (LBTEST) for LBSCAT = for PRX-102 is Negative; otherwise the status will be determined based on the result of ‘IgG Immunodepletion (Pos/Neg)’ : Positive or Negative,
- b. Neutralizing Antibody = the result of ‘Neutralizing Antibody (Pos/Neg)’ (LBTEST): Positive or Negative,
- c. IgE = the result of ‘IgE Screening (Presumptive Pos/Neg)’ (LBTEST): Positive or Negative.

9.7. Vital Signs

The vital signs (systolic and diastolic blood pressure, pulse rate, temperature, and respiratory rate) will be summarized overall and by gender, by visit for pre-dose, 30, 60, and every hour after infusion. The change and percent change from pre-dose to each post-dose (30, 60 minutes etc. after infusion) will be summarized as well for each visit.

9.8. Concomitant Medication

The summary table for all concomitant medications reported during the study, and coded by World Health Organization (WHO) Drug Dictionary 2018, will be summarized for overall and by gender

The medication used for pain will be identified based on the classification on the eCRF. These pain medications will be summarized for overall and by gender, by descriptive statistics, i.e. the count and percentage of the subjects with each medication by standardized medication name within medication class.

Additionally, the number of patients treated with ACEi and/or ARBs while on pegunigalsidase alfa will be summarized by descriptive statistics for overall and by gender.

Listing of medication will include start and end date and whether the drug was taken prior to 1st infusion of pegunigalsidase alfa.

9.9. X-Ray

Results of x-ray will be listed.

9.10. Pregnancies

Results of pregnancy tests will be listed.

10. ANALYSIS OF EFFICACY ENDPOINTS

10.1. Estimated Glomerular Filtration Rate (eGFR_{CKD-EPI})

The change in eGFR will be examined by comparing the change in annualized slope of eGFR while on Replagal[®] (“Pre-switch”) to the slope in eGFR after switch to pegunigalsidase alfa treatment (“Post-switch”). Due to the nature of the prevalence of this rare disease and the variability of disease state between patients, using patients as their own control provides a rational method for clinical and statistical analysis of this patient population.

10.1.1. eGFR Estimation

eGFR will be calculated based on the value of the serum creatinine values according to the CKD-EPI formula:

$$\text{eGFR (mL/min/1.73 m}^2\text{)} = 141 \times \min(\text{Scr}/\kappa, 1)^\alpha \times \max(\text{Scr}/\kappa, 1)^{-1.209} \times 0.993^{\text{Age}} \times 1.018 \text{ [if female]} \times 1.159 \text{ [if black / African American]}$$

where Scr is serum creatinine (mg/dL), κ is 0.7 for females and 0.9 for males, α is -0.329 for females and -0.411 for males, min indicates the minimum of Scr/ κ or 1, and max indicates the maximum of Scr/ κ or 1. (Note to programmer: serum creatinine can be found in two categories (CHEMISTRY and ENZYMATE) in the SDTM. Both will be used to estimate eGFR)

The age should be the actual age when the subject’s serum creatinine is collected, the calendar age at each timepoint should be used in the formula to be consistent with that in the Electronic Data Capture (EDC) system.

The eGFR will not be calculated again if its value is available from the CRF system (all eGFR values are calculated for the screening assessments).

10.1.2. Annualized Change in eGFR (Slope)

The annualized change in eGFR per subject will be estimated using a linear regression:

$$\text{eGFR} = \alpha + \beta \times [\text{time in year}], \text{ based on all visits where eGFR is available.}$$

The slope β (mL/min/1.73 m² / year) will be an estimate of the subject's annualized change in eGFR. The "[time in year]" in the formula is the time, in year, from "baseline" to the respective visit, and will be estimated by (date of the visit – date of baseline)/365.25.

The eGFR obtained in Visit 1 pre-infusion of pegunigalsidase alfa will be included in the calculation of both slopes, as the last data point to be used in the pre-switch annualized slope calculation, and the first data point to be used in the post-switch annualized slope calculation.

Any eGFR data obtained more than 730 days (approximately 24 months) prior to Screening visit will not be used in estimating the pre-switch annualized slope. The exact exclusion rule

is: data will not be used if the time in days from the date of evaluation to the date of screening is greater than 730 days. The "pre" switch slope calculation will include all eGFR values with less than 730 days before Screening, eGFR values during screening period (about 3 months), and pre-infusion eGFR at visit 1.

10.1.3. eGFR and eGFR Slope Analysis

The eGFR values at all visits, and the pre- and post-switch eGFR slopes, along with the difference between the pre- and post-switch eGFR slopes will be presented per individual subject.

The change in eGFR from baseline up to 12 months will be summarized by descriptive statistics.

The eGFR slopes pre- and post-switch, and the change in eGFR slopes from pre- to post-switch, will be summarized by descriptive statistics. The comparison of eGFR slopes between pre- and post-switch will be made by using a paired t-test. A 95% Confidence Interval (CI) will be presented as well.

The analyses in this section will be repeated for the subgroups described in Section 7.4 and the following additional subgroups:

1. Annualized slope of eGFR \leq and $>$ -3 mL/min/1.73 m²/year at baseline (i.e. pre-switch eGFR slope),
2. Baseline eGFR \leq and $>$ 60 mL/min/1.73 m² (Visit 1 or, when not available, the last measurement before receiving the first treatment with pegunigalsidase alfa),
3. Baseline UPCR based on the categories defined in Section 10.4,
4. Usage of ACEi or ARBs treatment pre-switch (Yes/No).

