7. STATISTICAL ANALYSIS METHODS AND ISSUES

7.1. Statistical Methods

Descriptive statistics, namely sample size (n), mean and its standard error, standard deviation, median, minimum and maximum for continuous variables, and count and percentage for categorical variables, will be provided.

Statistical comparison of the efficacy endpoints, the estimated slopes of eGFR, between pre and post treatment of pegunigalsidase alfa will be performed using parametric and/or non-parametric approaches and are to be described in detail in Section 10 of this document.

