11. LIST OF TABLES, FIGURES AND DATA LISTINGS

11.1. Statistical Tables

The statistical tables will be generated using SAS version 9.4. In general, the sample size (n), minimum, and maximum will be presented by whole number. The mean and its standard error, standard deviation, and median will be rounded and presented to one decimal place. For some values with meaningful decimal digits, their mean, standard error of mean, standard deviation, and median will be rounded to more than one decimal place when necessary. The count will be the whole number. The percentage will be rounded and presented to one decimal place. The p-value will be rounded to three decimal places. While the p-value is less than 0.001, it will be presented as <0.001.

Tables for the Per Protocol population will be generated only in case that the Per Protocol and the Efficacy population are different. In such cases, “PP” will be added to the table number to distinguish it from the efficacy population.

Disposition of Subjects, Baseline Characteristics, Exposure and Compliance:

Number	Title	Population
14.1.1	Disposition of Subjects for Overall	All
14.1.2.1	Demographics for Overall and by Gender	Safety
14.1.2.2	Demographics for Overall and by Gender	EP, PP
14.1.3.1	Treatment Compliance for Overall and by Gender	Safety
14.1.3.2	Treatment Compliance for Overall and by Gender	EP, PP
14.1.4.1.1	Baseline Characteristics by Overall and by Gender	Safety
14.1.4.2.1	Baseline Characteristics by Baseline FD Classification and Treatment Emergent ADA	Safety
14.1.4.1.2	Baseline Characteristics for Overall and by Gender	EP, PP
14.1.4.2.2	Baseline Characteristics by Baseline FD Classification and Treatment Emergent ADA	EP, PP
14.1.5.1.1	Fabry Disease Medical History for Overall and by Gender	Safety
14.1.5.1.2	Fabry Disease Medical History for Overall and by Gender	EP, PP
14.1.5.2.1	Other Medical History for Overall and by Gender	Safety
14.1.5.2.2	Other Medical History for Overall and by Gender	EP, PP
14.1.6.1.1	Exposure Overall and by Gender	Safety
14.1.6.1.2	Exposure Overall and by Gender	EP, PP
14.1.7.1.1	Number of Infusions and Duration Overall	Safety
14.1.7.1.2	Number of Infusions and Duration for Overall	EP, PP

Efficacy:

Number	Title	Population
14.2.1.1.1	Kidney Functions (eGFR and eGFR Slope) for Overall and by Gender	EP, PP
14.2.1.1.2	Kidney Functions (eGFR and eGFR Slope) by Baseline FD Classification and Treatment Emergent ADA	EP, PP

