14.2.1.2	Kidney Functions (eGFR and Slope) Per Patient Listing	EP, PP
14.2.1.3.1	Kidney Functions (eGFR Slope) by Baseline eGFR Slope and Baseline eGFR Categories	EP, PP
14.2.1.3.2	Kidney Functions (eGFR Slope) by Baseline UPCR Categories	EP, PP
14.2.1.3.3	Kidney Functions (eGFR Slope) with/without ACEi or ARBs treatment pre-switch	EP, PP
14.2.1.4	Kidney Functions (eGFR Slope) Therapeutic Goal Analysis	EP, PP
14.2.1.5	Kidney Functions (eGFR Slope) by kidney disease Severity Shift from Pre-Switch to Post-Switch	EP, PP
14.2.2.1.1.1	Plasma Lyso-Gb3 Concentrations for Overall and by Gender	EP, PP
14.2.2.1.1.2	Plasma Lyso-Gb3 Concentrations by Baseline FD Classification and Treatment Emergent ADA	EP, PP
14.2.2.1.2	Plasma Lyso-Gb3 Concentrations including Change from Baseline Per Patient Listing	EP, PP
14.2.2.1.3	Number of Subjects with 20%, 30%, 40% and 50% Reduction from Baseline in Plasma Lyso-Gb3 Concentrations for Overall	EP, PP
14.2.2.2.1	Plasma Gb3 Concentrations for Overall and by Gender	EP, PP
14.2.2.2.2	Plasma Gb3 Concentrations by Baseline FD Classification and Treatment Emergent ADA	EP, PP
14.2.2.3.1	Urine Lyso-Gb3 Concentrations for Overall and by Gender	EP, PP
14.2.2.3.2	Urine Lyso-Gb3 Concentrations by Baseline FD Classification and Treatment Emergent ADA	EP, PP
14.2.2.4.1.1	Short Form Brief Pain Inventory (BPI) for Overall and by Gender	EP, PP
14.2.2.4.1.2	Short Form Brief Pain Inventory (BPI) by Baseline FD Classification and Treatment Emergent ADA	EP, PP

Number	Title	Population
14.2.2.4.2	Short Form Brief Pain Inventory (BPI) - Shift from Baseline for Overall	EP, PP
14.2.2.5.1	Cardiac MRI (LVM, LVMi, and %EF) for Overall and by Gender	EP, PP
14.2.2.5.2	Cardiac MRI (Left Ventricular Fibrosis Segments) – Shift from Baseline for Overall	EP, PP
14.2.2.6	Echocardiogram Report – Shift from Baseline for Overall and by Gender	EP, PP
14.2.2.7.1	Stress Test for Overall and by Gender	EP, PP
14.2.2.7.2	Stress Test - Shift from Baseline for Overall and by Gender	EP, PP
14.2.2.8.1	Quality of Life EQ-5D-5L (Overall Health Score) for Overall and by Gender	EP, PP
14.2.2.8.2	Quality of Life EQ-5D-5L (Qualitative Assessments) for Overall and by Gender	EP, PP
14.2.2.8.3	Quality of Life EQ-5D-5L (Qualitative Assessments) - Shift from Baseline for Overall	EP, PP
14.2.2.9.1	Urine Protein/Creatinine Ratio (UPCR) for Overall and by Gender	EP, PP
14.2.2.9.2	Urine Protein/Creatinine Ratio (UPCR) - Shift from Baseline for Overall	EP, PP

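### SAP 10.1.3 tests the change in eGFR slope within subgroups cut on the estimated pre-switch slope, so regression to the mean biases both subgroup tests and confidence intervals

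*SAP*

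**What the plan says.** Under SAP 10.1.2 each patient gets two separate least-squares slopes, one before and one after the switch. They have one observation in common: "The eGFR obtained in Visit 1 pre-infusion of pegunigalsidase alfa will be included in the calculation of both slopes".

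SAP 10.1.3 then states: "The comparison of eGFR slopes between pre- and post-switch will be made by using a paired t-test". It adds: "A 95% Confidence Interval (CI) will be presented as well". The next instruction is: "The analyses in this section will be repeated for the subgroups described in Section 7.4 and the following additional subgroups". The first additional subgroup is the annualised slope, split at −3 mL/min/1.73 m²/year, "at baseline (i.e. pre-switch eGFR slope".

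The output is listed in SAP 11.1 as Table 14.2.1.3.1, "Kidney Functions (eGFR Slope) by Baseline eGFR Slope and Baseline eGFR Categories", for the efficacy and per-protocol populations. The same section sets a format for p-values: "The p-value will be rounded to three decimal places".

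Protocol 6.3.1 (inclusion criterion 7) requires at least two historical creatinine values. The flow chart adds Screening, Visits A and B, and Visit 1. With no scheduled value missing, a pre-switch slope may thus rest on as few as six points. Neither document mentions regression to the mean for this subgroup.

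**The concern.** Patients are sorted by an estimate that contains error, and that estimate is then subtracted from the post-switch slope. Those at or below −3 include a surplus of patients whose pre-switch slope came out too steep by chance. Those above −3 include a surplus whose slope came out too flat. The post-switch slope does not repeat that error, so the first group tends to look improved and the second worsened, whatever the drug does.

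The shared Visit 1 value adds to this. A Visit 1 reading that is low by chance steepens the pre-switch slope and flattens the post-switch slope.

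Within these two subgroups, zero mean change is therefore the wrong reference, and the p-value and CI do not have their nominal properties. The cut of −3 is also the boundary of stable kidney disease in SAP 10.1.4. A reader could easily take the table as benefit in decliners and harm in stable patients. No control arm would reveal the artefact.

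**Working it through.** The plan gives no figure to reproduce: SAP 4.1 says that no formal sample size calculation was done.

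**Inputs from the documents.** n = 22. Creatinine at Screening, A, B and Visit 1 (−3, −2, −1, 0 months). Post-switch creatinine at Visits 1, 3, 5, 7, 9, 11, 14, 16, 18, 20, 22, 24 and 27, taken as weeks 0, 4, 8, 12, 16, 20, 26, 30, 34, 38, 42, 46 and 52. Two-sided 5% is implied by the 95% CI.

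**Assumed inputs (not in the documents).** Central case: mean true slope −3, between-patient slope SD 3, within-patient eGFR SD 5, two historical values at −27 and −15 months from Visit 1, and true change zero in every patient.

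**Step 1: error of the pre-switch slope.** Times in years: −2.25, −1.25, −0.25, −0.167, −0.083, 0. Mean −0.667; sum of squares about the mean 6.722 − 6 × 0.667² = 4.056. Error variance = 25 / 4.056 = 6.16 (SE 2.5).

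**Step 2: error of the post-switch slope.** Mean time 0.4835 years; sum of squares about the mean 1.236. Error variance = 25 / 1.236 = 20.2 (SE 4.5).

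**Step 3: covariance through Visit 1.** Weight in the pre-switch slope: 0.667 / 4.056 = 0.164. Weight in the post-switch slope: −0.4835 / 1.236 = −0.391. Covariance = 25 × 0.164 × (−0.391) = −1.61.

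**Step 4: regression of the post-switch on the pre-switch estimate.** b = (slope variance + covariance) / (slope variance + pre-switch error variance) = (9 − 1.61) / (9 + 6.16) = 0.487.

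**Step 5: expected change in a group.** Under joint normality, E(post − pre | group) = (1 − b) × (mean slope − E(pre-switch estimate | group)). With the mean at the cut, the last bracket for the ≤ −3 group is √15.16 × √(2/π) = 3.894 × 0.798 = 3.107.

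- ≤ −3: 0.513 × 3.107 = **+1.59**
- > −3: **−1.59** by symmetry
- Without the shared value: b = 9 / 15.16 = 0.594, giving ±1.26. The shared point adds about 0.33; selection is the main cause.

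**Step 6: test behaviour by simulation.** With n = 22 and no effect, the central case gives about 15% two-sided rejection in each half. The 95% CI contains zero in about 85% (≤ −3) and 84% (> −3) of trials. The all-patient test rejects in about 5%, with mean change 0.0. The mean change in the ≤ −3 group is positive in about 84% of trials.

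**Step 7: sensitivity to the assumptions** (history at −27/−15 months unless stated).

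| Mean slope | Slope SD | eGFR SD | Change in ≤ −3 | Change in > −3 | Two-sided rejection |
|---|---|---|---|---|---|
| −3 | 4 | 3 | +0.5 | −0.5 | 7–8% |
| −3 | 3 | 5 | +1.6 | −1.6 | 15% |
| −3 | 2 | 8 | +3.6 | −3.6 | 27% |
| −1 | 2 | 8 | +4.9 | −2.4 | 30% in ≤ −3 |
| −3 | 3 | 5, history −15/−9 | +3.6 | −3.6 | about 43% |

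The two halves mirror each other only when the mean slope equals the cut. At central SDs they are +2.3/−1.0 at mean −1 and +1.0/−2.3 at mean −5. A separate calculation with other assumed historical dates gave 0.3 to 5.4 in absolute size and 7–36% rejection. With measurement error set almost to zero, the bias vanished and rejection returned to about 5%, so slope-estimation error is the cause.

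**The case against.** The strongest reply concerns consequence. Safety is the primary objective, and this is one of several eGFR splits. No alpha allocation or decision rule is attached, and individual pre- and post-switch slopes are shown as well. The protocol synopsis says that data will not be analysed inferentially, although SAP section 2 makes the SAP prevail. All this stands, and it limits the harm to how this table is read. It does not make the planned p-value or CI correct.

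One could also keep the CI with a footnote, because it shows how imprecise groups of about 11 are. But the interval is centred on a biased quantity, and the SD and n already convey the imprecision.

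Four stronger readings are tempting but not supported:

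- **That decliners will always appear to improve.** The sign holds in expectation. In the central case about one trial in six shows the opposite sign in the ≤ −3 group.
- **That the overall pre/post comparison is spoiled by this selection.** It is not, since no patient is selected on the slope there.
- **That a faulty non-parametric version is also planned.** SAP 7.1 says comparisons "will be performed using parametric and/or non-parametric approaches" but leaves the detail to Section 10, and 10.1.3 names only the paired t-test.
- **That the goal and shift tables of SAP 10.1.4 show the same defect in full.** They carry no test or CI. In the central case, about 70–90% of their departure from perfect class retention comes from the imprecise post-switch slope (SE 4.5 against 2.5), not from selection.

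**Conclusion.** The point holds for additional subgroup 1 of SAP 10.1.3: its p-values and CIs are wrong as planned. The sign of the expected bias follows from the design and needs only that the pre-switch slope be estimated with error. The size does depend on assumed SDs, mean slope and historical dates. It is about ±1.6 mL/min/1.73 m²/year with about 15% rejection in the central case. Over the values tried with history at −27/−15 months it runs from about 0.5 with 7% rejection to about 5, and rejection exceeds 40% when the two historical values fall at −15 and −9 months.

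This should be fixed, but it is a problem of interpretation in one secondary table and not a threat to the trial's main conclusions.

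**What to change.** 1. For additional subgroup 1 (Table 14.2.1.3.1), remove the paired-test p-value and the 95% CI for the change. Report n, pre-switch slope, post-switch slope and change descriptively.
2. Add a footnote to that table: patients are grouped by their estimated pre-switch slope, so apparent improvement in the ≤ −3 group and apparent worsening in the > −3 group are expected without any treatment effect.
3. Add one sentence under the SAP 10.1.4 goal and shift tables: error in the two estimated slopes alone moves patients between classes, so the row percentages are not by themselves evidence of benefit or harm.
4. Add a similar caution for the baseline eGFR ≤ / > 60 subgroup, because the Visit 1 value both defines the group and enters both slopes.

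The cut points stay as they are. The cost is the removal of one subgroup p-value and CI and a few lines of text, with no new data and no new analysis. The downside is that results in decliners will look less favourable than the plan as written would make them look.
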